#### **5.2.4.2 Other Laboratory Parameters**

Quantitative data for all other laboratory parameters will be presented using descriptive statistics of values and absolute changes from baseline to each visit. Shift tables will be presented when applicable.

Other laboratory parameters include urinalysis, inflammatory markers, cytokine panel (The cytokine panel will include but is not limited to IFN- $\gamma$ , IL-2, IL-4, IL-6, IL-8, and TNF- $\alpha$ ).

#### **5.2.4.3 Vital Signs**

Descriptive statistics for semi-recumbent vital signs including heart rate (HR), systolic and diastolic blood pressure (BP), respiratory rate (RR), body temperature at each visit will be presented.

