Laser imaging and capsaicin challenge ⁴	X	X				X					X	X						X	X ¹⁶	X ¹⁶

Abbreviations: AE = adverse event; CRU = Clinical Research Unit; D = day; DBF = dermal blood flow; ECG = electrocardiogram; EoS = End of Study; EoT = End of Treatment; ET = Early Termination; FSH = follicle-stimulating hormone; H = hour; HBV = hepatitis B virus; HCV = hepatitis C virus; HIV = human immunodeficiency virus; IM = intramuscular; IMP = investigational medicinal product; LSCI = Laser Speckle Contrast Imaging; MRI = magnetic resonance imaging; PBMC = peripheral blood mononuclear cell; PD = pharmacodynamic; SAE = serious adverse event; SD = standard deviation; SRN = Screening; TC = telephone call; V = visit

1. The Investigator may perform visits outside of the scheduled study visits (unscheduled visits) listed in the table to conduct evaluations or assessments required to protect the well-being of the participant.
2. Screening and V1 visits can be rescheduled, and Screening window may be extended.
3. AEs/SAEs recording from time of informed consent up to and including Follow-up or ET.
4. On IMP administration days, all laboratory, PD, and capsaicin assessments are to be performed prior to IMP administration.
5. After each IMP administration, (a) participants will stay for 6 hours (± 2 hours) after injection for safety observation (except for sentinel participants who will stay for 24 hours after the first dose), (b) participants (except the sentinels' first dose) will have an approximately 24-hour onsite safety review including review of vital signs, temperature, diary, AEs, and medications, (c) all participants will have a telephone call approximately 48-hours post IMP injection for safety check including AE and medication review, and (d) all participants will complete a diary daily for 7 days, starting from the day of IMP administration.
6. On IMP administration days, vital signs (including temperature) will be measured before and after IMP administration.
7. Participants should be resting in a semi-recumbent position for at least 10 minutes before vital signs measurements. Semi-recumbent vital signs will include heart rate, systolic and diastolic blood pressure, respiratory rate, and body temperature.
8. Full neurological and physical examinations are to be performed during Screening, at Week 16 (EoT), Week 44 (EoS), and ET; brief (targeted) examinations may be performed at all other visits.
9. Laboratory assessments are detailed in Section 7.7 and Appendix 1.

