10. A diary will be dispensed on Day 1. Participants will complete it for 7 days daily, starting on the day of each administration of IMP.
11. For females of childbearing potential only, blood pregnancy test at Screening and urine test at other visits. For females of nonchildbearing potential in post-menopausal state, FSH at screening.
12. Inflammatory measures in blood will include but are not limited to C-reactive protein and erythrocyte sedimentation rate. At Screening only, antinuclear antibody, IgM rheumatoid factor, and anti-cyclic citrullinated peptide.
13. Cytokine blood samples will be collected pre-dose and approximately 6 hours (± 2 hours) post-dose, and only analyzed at the Investigator's discretion if clinically indicated; otherwise, they will be analyzed at the EoT visit. The cytokine panel will include but is not limited to IFN- γ , IL-2, IL-4, IL-6, IL-8, and TNF- α .
14. Antibody measures in blood, including but not limited to anti-CGRP target epitope, anti-UBITh, anti-CpG1, and isotyping of anti-CGRP antibodies.
15. A sample to be obtained as allowed by local regulations and participant consent.
16. After Week 16, LSCI assessment may no longer be required once the average capsaicin-induced DBF increase within that cohort has returned to baseline (i.e., DBF response ± 2 SD before administration of IMP within a cohort).
17. Historic MRI within 90 days of Screening may be accepted.
18. IMP should be administered to the opposite arm that was used to take blood. Alternate arms should be used for injection visits and the arm used for IMP administration should be recorded.
19. A blood sample to be obtained for HLA typing at any post-Week 16 visit as allowed by participant consent. Blood sample is only to be collected at one visit.

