### **4.0 General Consideration**

All analyses will be conducted using observed data only and no missing data will be imputed.

In general, the baseline value is defined as the last available value before the first injection of study dose.

All analysis and summary will be performed by dose group, defined as below:

- 100/100/100 $\mu$ g (8 active participants in cohort 1)
- 300/100/100 $\mu$ g (8 active participants in cohort 2)

- 300/300/300 $\mu$ g (8 active participants in cohort 3)
- 600/100/100 $\mu$ g (8 active participants in cohort 4)
- Placebo (8 participants from all cohorts)

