## 5.0 Statistical Analyses

### 5.1 Immunogenicity, Pharmacodynamics, and Exploratory Analyses

Efficacy analysis will be based on FAS. All analyses and plot will be performed by dose group for each visit and each timepoint unless otherwise specified. In general, summary of a variable (e.g., titer, CIDBF) will include baseline, actual value, and change (or percent change) from baseline when applicable. Summary plots will be done when applicable.

For qualitative assessments (e.g., titer value, CIDBF...), the distribution will be examined. If the distribution is similar to log normal, log transformation will be applied. In this case, geometric mean and GMR (Geometric Mean Ratio) will be presented in place of mean and difference. For model analysis, log transformed value will be used, analysis results will be presented after anti log transformation.

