#### **5.2.4.6 Electrocardiograms (ECGs)**

Descriptive statistics for triplicate ECG parameters and changes from baseline values at each visit will be presented. Shift from baseline to the worst postbaseline will be presented.

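### The SAP specifies no same-day pre-to-post change for vital signs, and it measures cytokine changes at injections 2 and 3 from before the first injection

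*SAP*

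**What the plan says.** The protocol's schedule (Table 1) labels both the vital-sign row and the cytokine row as pre- and post-IMP. Footnote 6 reads: "On IMP administration days, vital signs (including temperature) will be measured before and after IMP administration". Footnote 13 reads: "Cytokine blood samples will be collected pre-dose and approximately 6 hours (± 2 hours) post-dose". Cytokine samples not needed sooner for clinical reasons are still assayed: "otherwise, they will be analyzed at the EoT visit". The paired results should therefore exist for both.

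SAP 5.2.4.3 is one sentence on vital signs. It lists five parameters and ends "body temperature at each visit will be presented". SAP 5.2.4.2 includes the cytokine panel among the other laboratory parameters and plans "descriptive statistics of values and absolute changes from baseline to each visit". SAP 4.0 says which baseline: "the baseline value is defined as the last available value before the first injection of study dose".

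The SAP is more explicit elsewhere. For ECGs (5.2.4.6): "Descriptive statistics for triplicate ECG parameters and changes from baseline values at each visit will be presented". For the capsaicin challenge (5.1.2.1) it defines a within-visit change, each post-capsaicin reading minus the reading at minute 0 of the same visit.

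**The concern.** A reading before and a reading after the same injection support one natural contrast, the within-participant difference. It removes the participant's own level and anything that has changed since the start of the study. The SAP does not ask for it.

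For vital signs no change of any kind is specified, and nothing says how a dosing visit with two readings is to be tabulated. For cytokines a change is specified, but from a reference that suits only the first injection. At the second and third, a raised 6-hour value could reflect release after that injection, a level already raised before it, or both. Vital signs and clinical laboratory assessments belong to the primary safety endpoint of a first-in-human study, and whether the response changes with repeated dosing is a question these data could address.

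**Working it through.** The plan gives no figure to reproduce: the study is not powered and the safety summaries are descriptive. The check is a count, some algebra and a precision comparison.

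**Inputs from the documents.** Five vital signs: heart rate, systolic and diastolic pressure, respiratory rate, temperature (SAP 5.2.4.3). Six named cytokines: IFN-γ, IL-2, IL-4, IL-6, IL-8, TNF-α (SAP 5.2.4.2; the list is not exhaustive). Three injections, on Days 1, 29 and 85 (protocol Table 1). Eight participants per dose group, including pooled placebo (SAP 4.0). The column positions of the cytokine row in Table 1 may have shifted in text extraction, so I rely on the row label and footnote 13, which do not restrict the 6-hour sample to the first dose.

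**1. Contrasts available and specified.**
- Available: (5 + 6) × 3 = 33.
- Vital signs: 5 × 3 = 15, none specified.
- Cytokines at injections 2 and 3: 6 × 2 = 12, none specified.
- Cytokines at injection 1: 6 × 1 = 6. Baseline is normally the Day 1 pre-dose sample, so change from baseline at the 6-hour sample is the acute change, provided that sample is tabulated. The SAP does not say whether it is.
- No matching analysis: 15 + 12 = 27 of 33.

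**2. Age of the cytokine reference.** Day 29 − Day 1 = 28 days (4 weeks). Day 85 − Day 1 = 84 days (12 weeks).

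**3. What the specified cytokine change measures.** Let b be the Day 1 pre-dose value, d the drift since then and a the acute effect of the later injection. The pre-dose value is b + d and the 6-hour value is b + d + a.

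| Contrast | Result | With a = 1: d = −0.5 | d = 0 | d = 0.5 | d = 1 |
|---|---|---|---|---|---|
| 6 h minus Day 1 | a + d | 0.5 | 1 | 1.5 | 2 |
| Pre-dose minus Day 1 | d | −0.5 | 0 | 0.5 | 1 |
| 6 h minus that visit's pre-dose | a | 1 | 1 | 1 | 1 |

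Only the last row isolates a whatever the drift. The values of d are illustrative; the documents give none.

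**4. What pairing adds.** Suppose pre- and post-dose values are tabulated separately but no change is. A reader can subtract the two means. Without the within-participant correlation ρ, however, the only standard error available treats the means as independent: SD × √(2/8) = 0.50 SD. The paired standard error is SD × √(2(1 − ρ)/8):
- ρ = 0.3: 0.42 SD
- ρ = 0.5: 0.35 SD
- ρ = 0.7: 0.27 SD
- ρ = 0.9: 0.16 SD

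The range of ρ, and equal SDs before and after dosing, are assumptions.

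**The case against.** Several defences have force.

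- **The acute effect is not wholly lost.** A reader might infer that it is never estimated. The documents do not support that. Injection 1 is normally covered for cytokines, as shown above. At later injections SAP 5.2.4.2 plans values as well as changes; if pre-dose and 6-hour values appear separately, their mean difference on complete pairs is (a + d) − d = a. What is then missing is the paired SD or interval and the individual changes.
- **Pooling is not planned.** A reader might also infer that pre- and post-dose readings will be averaged within a visit, which would turn a into a/2 + d. No passage says so, and the wording allows separate columns. The gap is an undefined timepoint and contrast.
- **Other data cover acute tolerability in part.** Vital signs are also scheduled the day after each injection (V1a, V3a, V6a). Solicited reactions are counted by participant and by injection (SAP 5.2.3.3), temperature is recorded in a 7-day diary, and adverse events are summarised by participant. It would be wrong to conclude that one participant's reaction could not be seen. These sources do not, however, summarise measured blood pressure, heart rate or respiratory rate just after dosing, or cytokine concentrations at 6 hours.
- **A general rule might apply.** SAP 5.1 states: "All analyses and plot will be performed by dose group for each visit and each timepoint unless otherwise specified". That section governs immunogenicity, pharmacodynamic and exploratory analyses on the FAS. Section 5.2, on the safety set, does not repeat it, and it would not create a change score in any case.
- **Placebo gives some control.** Setting the active column beside placebo removes drift common to both, but not drift caused by earlier active doses.

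Two limits also apply. The documents do not state why the paired readings are taken; that they serve to show acute effects is an inference. And only the protocol's synopsis and schedule were available, so its full text may define timepoints that the SAP leaves open.

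**Conclusion.** The point holds as a gap in specification for vital signs and as an unsuitable reference for cytokines after the first dose. No same-day change is specified for vital signs at any injection. For cytokines at injections 2 and 3, the specified change equals the acute effect plus drift since Day 1, and isolates the acute effect only if drift is zero. Together this is 27 of 33 contrasts, with 6 more depending on whether the Day 1 post-dose sample is tabulated.

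The cytokine result is algebraic and needs no assumed figure, only the reading of footnote 13 that the 6-hour sample is taken at every dose. The precision gain from pairing, a standard error of 0.42 to 0.16 SD against 0.50 SD, rests on an assumed correlation of 0.3 to 0.9. The trial's conduct and data collection are unaffected.

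**What to change.** In SAP 5.2.4.3, tabulate pre-dose and post-dose vital signs separately at dosing visits. Summarise the within-participant change, post-dose minus same-day pre-dose, by dose group and injection. At other visits, add change from the Day 1 baseline.

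In SAP 5.2.4.2, summarise the 6-hour cytokine value relative to the pre-dose sample of the same dosing visit, for each injection, and keep change from Day 1 for the pre-dose samples. Table 1 gives the pre-IMP part of the visit a window of −3 days, so the SAP should say that this sample is the reference even if it was not drawn on the injection day.

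Counts of participants with changes beyond prespecified limits would be a useful but optional addition.

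The cost is SAP wording and slightly longer safety tables. All the readings are already scheduled, and no visit, sample or blinding arrangement changes.

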#### **5.2.4.4 Neurological Examinations**

Results will be summarized or listed.

#### **5.2.4.5 Physical Examinations**

Results will be summarized or listed.

#### **5.2.4.6 Electrocardiograms (ECGs)**

Descriptive statistics for triplicate ECG parameters and changes from baseline values at each visit will be presented. Shift from baseline to the worst postbaseline will be presented.

### **5.2.5 Other Safety Parameters**

#### **5.2.5.1 Height and Weight**

Descriptive summary will be done.

#### **5.2.5.2 Pregnancy Test**

Positive results will be listed.

### **5.3 Other Analyses**

#### **5.3.1 Study Participants**

##### **5.3.1.1 Disposition of Participants**

The total number of participants will be summarized below.

- Participants who were screened (who signed informed consent)

Number and percentage of participants in each of the following categories will be summarized.

- Participants who were randomized (this is denominator for the percentages described below)
- Participants who received at least one dose of study drug
- Participants who completed treatment period (Week 16)
- Participants who discontinued during the treatment period
  - Reasons for treatment discontinuation (based on reasons reported on CRF)
- Participants who completed the study
- Participants who discontinued from the study
  - Reasons for study discontinuation (based on reasons reported on CRF)

Number of participants in each analysis population will be summarized. Participants excluded from analysis will be listed.

In addition, reasons for screen failure will be summarized.

##### **5.3.1.2 Protocol Deviations**

Major protocol deviations will be summarized.

#### **5.3.1.3 Demographics and other Baseline Characteristics**

##### **5.3.1.3.1 Demographics**

Demographic parameters (age, gender, race, and ethnicity) will be summarized.

##### **5.3.1.3.2 Baseline characteristics**

Baseline parameters (height, body weight, BMI) will be summarized.

### 5.3.1.4 Medical History

Medical history and surgical history that are not ongoing at the trial initiation, and medical history that are ongoing at the trial initiation will be summarized separately. The number and percentage of participants will be tabulated by MedDRA SOC and PT. The actual version of MedDRA will be noted in the statistical tables and clinical study report.

### 5.3.1.5 Prior and Concomitant Medications

A prior medication is defined as any medication taken prior to the start of study treatment. A concomitant medication is defined as any medication taken after the start of study treatment (i.e., any medication that started prior to the study treatment and continued to be taken after the study treatment or any medication that started after the study treatment).

Prior and concomitant medications will be coded using the World Health Organization (WHO) Drug Dictionary. The actual version of WHO will be noted in the statistical tables and clinical study report. The number and percentage of participants reporting prior or concomitant medications will be summarized separately by Anatomical Therapeutic Chemical (ATC) 1st level class and preferred drug name. If more than one medication is coded to the same preferred drug name for the same participant, the participant will be counted only once for that preferred drug name.

## 6.0 Additional details not mentioned in the protocol

Additional details and specifications have been included in this SAP to allow for better understanding of the intended methods. Additional analyses (including exploratory and subgroup assessments) for select variables have been added. Additional sensitivity analyses will be conducted to explore any effects related to the presence of data outliers.

## 7.0 Version History

SAP Version	Approval Date	Change	Rationale
1	17 May 2023	Not Applicable	Original version

Statistical Analysis Plan UB-313-101  
UBITh® CGRP Immunotherapeutic Vaccine  
Version 2.0 – 7 November 2023

2	Added AUC above baseline for anti-CGRP antibody titers in section 5.1.1.4.	To adjust for baseline.
	Added $C_{max}$ for anti-CGRP antibody titers in section 5.1.1.4.	To capture maximum titer level.
	Added text for CI DBF AUC in section 5.1.2.3.	Updated for clarity.
	Moved cytokine release from section 5.2.4.2 to section 5.1.3.4.	Updated for clarity.

## Appendix 1 List of Abbreviations

Abbreviation	Definition
ADA	Anti-drug antibody
AE	Adverse event
AESI	Adverse event of special interest
ANCOVA	Analysis of Covariance
BP	Blood pressure
CI	Confidence interval
COVID-19	Coronavirus disease 2019
CRF	Case report form (electronic or paper)
CRO	Contract research organization
DBP	Diastolic blood pressure
ECG	Electrocardiogram
EOS	End of study
EOT	End of treatment
FIH	First-in-human
GMR	Geometric Mean Ratio
HR	Heart rate
IMP	Investigational Medicinal Product
MedDRA	Medical Dictionary for Regulatory Activities
NA	Not applicable
NCS	Not clinically significant
PE	Physical examination
PD	Pharmacodynamic
PP	Pulse pressure
PT	Preferred term
SAE	Serious adverse event

Statistical Analysis Plan UB-313-101  
UBITh® CGRP Immunotherapeutic Vaccine  
Version 2.0 – 7 November 2023

Abbreviation	Definition
SS	Safety analysis set
SAP	Statistical analysis plan
SD	Standard deviation
SOC	System organ class
TEAE	Treatment-emergent adverse event
VS	Vital signs

## Appendix 2 MedDRA Terms for AESI

Preferred Term Code	Preferred Term	Primary System Organ Class Code	Primary System Organ Class
10047340	Vertigo	10013993	Ear and labyrinth disorders
10010774	Constipation	10017947	Gastrointestinal disorders
10028034	Mouth ulceration	10017947	Gastrointestinal disorders
10030985	Oral mucosa bleeding	10017947	Gastrointestinal disorders
10042128	Stomatitis	10017947	Gastrointestinal disorders
10016256	Fatigue	10018065	General disorders and administration site conditions
10022052	Injection site bruising	10018065	General disorders and administration site conditions
10022061	Injection site erythema	10018065	General disorders and administration site conditions
10022075	Injection site induration	10018065	General disorders and administration site conditions
10022086	Injection site pain	10018065	General disorders and administration site conditions
10022093	Injection site pruritus	10018065	General disorders and administration site conditions
10022094	Injection site rash	10018065	General disorders and administration site conditions
10022095	Injection site reaction	10018065	General disorders and administration site conditions
10053425	Injection site swelling	10018065	General disorders and administration site conditions
10030095	Oedema	10018065	General disorders and administration site conditions
10042674	Swelling	10018065	General disorders and administration site conditions
10002198	Anaphylactic reaction	10021428	Immune system disorders
10002218	Anaphylaxis	10021428	Immune system disorders
10020751	Hypersensitivity	10021428	Immune system disorders
10028810	Nasopharyngitis	10021881	Infections and infestations
10028334	Muscle spasms	10028395	Musculoskeletal and connective tissue disorders
10001760	Alopecia	10040785	Skin and subcutaneous tissue disorders
10002424	Angioedema	10040785	Skin and subcutaneous tissue disorders
10005191	Blister	10040785	Skin and subcutaneous tissue disorders
10064579	Exfoliative rash	10040785	Skin and subcutaneous tissue disorders
10037087	Pruritus	10040785	Skin and subcutaneous tissue disorders
10037844	Rash	10040785	Skin and subcutaneous tissue disorders
10037855	Rash erythematous	10040785	Skin and subcutaneous tissue disorders
10037876	Rash papular	10040785	Skin and subcutaneous tissue disorders
10037884	Rash pruritic	10040785	Skin and subcutaneous tissue disorders
10046735	Urticaria	10040785	Skin and subcutaneous tissue disorders

